#### 10.5 STATISTICAL ANALYSES

## 10.5.1 General Approach

The fraction of all evaluable participants who experience clinical benefit (CR+PR +SD>16 weeks) will be reported along with a confidence interval.

## 10.5.2 Analysis of the Primary Endpoint

The fraction of evaluable participants who experience clinical benefit will be reported along with a 95% two-sided confidence interval.

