#### 10.3 SAMPLE SIZE DETERMINATION

The primary objective of this trial is to determine if the CR, PR and SD > 16 weeks (clinical benefit) rate will be adequate using Minnelide without stratification for dose. The trial will be conducted using a Simon optimal two-stage phase II trial design [20][19] to rule out an unacceptably low clinical benefit rate of 20% (p0=0.20) in favor of an improved clinical benefit rate of 40% (p1=0.40). With alpha=0.10 (probability of accepting a poor treatment=0.10) and beta=0.20 (probability of rejecting a good treatment=0.20), the first stage will enroll a total of 12 evaluable participants. If 0-2 of these 12 participants have clinical benefit, then no further participants will be accrued. If 3 or more of the first 12 participants have clinical benefit, then accrual would continue until a total of 25 evaluable participants have been enrolled. As this is a rare participant population, trial accrual may continue for up to 15 participants while this determination is being made, but no new participants may be accrued to the trial once it is known that this criteria has not been met. If single agent activity is insufficient to meet criteria for study continuation, consideration will be given to exploring combination therapy including Minnelide in this population. If there are 3-7 participants with clinical benefit out of 25 participants, this would be an uninterestingly low clinical benefit rate. If there are 8 or more of 25 (32%) who experienced clinical benefit, this would be sufficiently interesting to warrant further study in later trials. Under the null hypothesis (20% clinical benefit rate), the probability of early termination is 55.8%.

It is expected that approximately one participant may initiate treatment on this trial every 1-2 months; thus, accrual to the trial may be completed in 3 years. In order to allow for screen failures and a small number of inevaluable participants, the accrual ceiling will be set at 55 participants.

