#### 10.4 POPULATIONS FOR ANALYSES

Intention to treat: any participants who enroll onto the trial and provide consent and who receive at least one dose of the assigned agent will be included in the efficacy and safety evaluations.

Version Date: 7/10/2025

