## **10.4.2** Evaluable for objective response:

Only those participants who have measurable disease present at baseline, have received at least one cycle of therapy, and have had their disease re-evaluated will be considered evaluable for objective response. These participants will have their response classified according to the definitions stated below. (Note: Participants who exhibit objective disease progression prior to the end of cycle 1 will also be considered evaluable.)

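### The 3/12 gate, the 8/25 rule and the primary estimate count only evaluable participants, a set not defined for disease control and at odds with the all-dosed efficacy population in Section 10.4

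*Combined protocol and SAP*

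**What the plan says.** Section 10.4 defines one efficacy population: consenting participants "who receive at least one dose of the assigned agent will be included in the efficacy and safety evaluations".

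The primary analysis uses a different unit. In Section 10.3 "the first stage will enroll a total of 12 evaluable participants", and after a pass at 3 or more of 12, accrual continues "until a total of 25 evaluable participants have been enrolled". Success is 8 or more of those 25. Section 10.5.1 reports "The fraction of all evaluable participants who experience clinical benefit", Section 10.5.2 says "The fraction of evaluable participants who experience clinical benefit will be reported along with a 95% two-sided confidence interval", and the interim look in Section 10.5.6 also counts 12 evaluable participants.

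Evaluable is defined for toxicity (10.4.1), objective response (10.4.2) and non-target disease response (10.4.3), but not for disease control. Under 10.4.2, participants with measurable disease who "have received at least one cycle of therapy, and have had their disease re-evaluated will be considered evaluable for objective response" qualify. There is one exception: "Participants who exhibit objective disease progression prior to the end of cycle 1 will also be considered evaluable". Section 10.4.3 has the same cycle and re-evaluation requirements for non-measurable disease. Section 3.1 explains inevaluable only as not evaluable for the primary endpoint, which is circular.

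The plan expects such cases. Section 10.3 sets the accrual ceiling at 55 to allow for screen failures and "a small number of inevaluable participants".

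**The concern.** Two analysts could each follow the text and report different denominators for the primary endpoint. If the 10.4.2 definition is imported, a treated participant with no post-baseline scan and no documented objective progression drops out, and accrual to 25 evaluable supplies a substitute. No section says how death, symptomatic deterioration, toxicity or withdrawal before the first scan counts for disease control.

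Such cases are foreseeable. Section 3.1 puts restaging at about every 8 weeks, and Section 12.3.3 gives a median survival of at most 3 months for this disease. End-of-treatment imaging (3.5) and the instruction in 6.3.3.3 to try to document progression after stopping will reduce the group. They cannot reach someone who dies or is lost before a scan.

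Almost everyone removed this way has shown no disease control. The exception would be a participant who stops in cycle 1 and later has a confirmed response. The same denominator governs the decision to continue, the success claim and the reported rate.

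**Working it through.** **Inputs from Section 10.3.** p0 = 0.20, p1 = 0.40, alpha 0.10, beta 0.20; continue if at least 3 of 12; success if at least 8 of 25; early termination 55.8% at p0.

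**Assumption.** f is the fraction of treated participants excluded as inevaluable, each counted as not having disease control. The documents give no value, so 5% and 10% are used. The expected number excluded by the time 25 are evaluable is 25f/(1 − f), which is 1.3 at 5% and 2.8 at 10%.

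**Step 1. Reproduce the design.** The probability of success is the sum over x = 3 to 12 of P(X1 = x | 12, p) × P(X2 ≥ 8 − x | 13, p).
- At p = 0.20: early termination P(X1 ≤ 2) = 0.558, as stated; type I error 0.0991.
- At p = 0.40: power 0.8151.

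The design is correct if the 12 and the 25 are complete sets.

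**Step 2. If 20% and 40% are rates among evaluable participants.** Type I error stays at 0.0991. What changes is the rate among those treated when 8 of 25 evaluable have disease control (exact Clopper-Pearson intervals):

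| Excluded | Rate among treated | 95% CI |
|---|---|---|
| 0 | 8/25 = 32.0% | 14.9–53.5% |
| 1 | 8/26 = 30.8% | 14.3–51.8% |
| 2 | 8/27 = 29.6% | 13.8–50.2% |
| 3 | 8/28 = 28.6% | 13.2–48.7% |

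**Step 3. If 20% is the rate among treated participants.** The rate among evaluable participants is then 0.20/(1 − f), and the Step 1 formula is applied at that rate:

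| f | Evaluable rate | P(at least 3 of 12) | Type I error |
|---|---|---|---|
| 0 | 0.2000 | 0.442 | 0.0991 |
| 5% | 0.2105 | 0.479 | 0.1250 |
| 10% | 0.2222 | 0.519 | 0.1578 |

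On this reading, the first 12 treated would fail the gate while the first 12 evaluable pass it in 3.7% of trials (f = 5%) or 7.7% (f = 10%). This takes each treated participant as excluded with probability f and otherwise controlled with probability 0.20/(1 − f).

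**Step 4. Price of counting everyone dosed.** If 40% was meant among evaluable participants, the all-treated rate is 0.40(1 − f). That is 0.38 at 5%, with power 0.759, and 0.36 at 10%, with power 0.694.

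**Step 5. If stage 1 has already been read on evaluable participants.** Keep that decision and require at least 8 of the first 25 treated. At a true 20% among treated, exact type I error is 0.1015 (f = 5%) or 0.1036 (f = 10%). It cannot exceed the single-stage value P(X ≥ 8 | 25, 0.20) = 0.1091.

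**The case against.** The strongest reply is that Sections 10.3, 10.5.1, 10.5.2 and 10.5.6 use evaluable consistently. On this view Section 10.4 is a general population with endpoint-specific subsets beneath it, and Section 3.1 points implicitly to 10.4.2 and 10.4.3. Evaluable-only analysis is also common in phase II. On that reading p0 and p1 most naturally describe evaluable participants, type I error is intact, and what remains is a modest reporting difference between wide, overlapping intervals.

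Much of this stands. Loss of error control is conditional on the treated reading, and the exclusion rate is assumed. The 3-month median makes unscanned participants plausible but does not give a rate for those enrolled. The all-treated fix also has a price: power can fall below the planned 0.80.

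It does not remove the conflict. The implied definition requires re-evaluation, so it confirms that unscanned participants drop out and are replaced. Section 10.4 says without qualification that dosed participants enter the efficacy evaluation, and the endpoint table in Section 10.1 places disease control in the whole study population. An evaluable-only primary analysis would still need a definition written for this endpoint and consistent with Section 10.4.

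**Conclusion.** The concern holds. The plan gives two incompatible denominators for its primary endpoint, and the one used by the decision rules lets treated participants without a scan be replaced. The effect on the reported rate is upward on either reading: about 1 to 3 percentage points at the success boundary with one to three exclusions. Type I error exceeds the planned 10% (12.5% or 15.8%) only if 20% is a rate among treated participants and 5% or 10% are excluded. Section 10.3 gives no source or reference population for 20% or 40%, so the documents do not settle which reading applies. This should be fixed, but it does not undermine the design, whose arithmetic is correct.

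**What to change.** Bring Section 10.4 into line with 10.3, 10.5.1, 10.5.2 and 10.5.6:

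- Every participant who receives at least one dose counts in both Simon stages and in the primary estimate.
- Those with no post-baseline disease assessment, whether from death, deterioration, toxicity, withdrawal or loss, count as not having disease control.
- The evaluable set of 10.4.2 becomes a sensitivity analysis, with the number excluded and the reasons reported.
- Section 10.3 states which population 20% and 40% describe. If they are evaluable-only rates, keep N = 25 and restate the all-treated power.
- If the stage 1 decision has already been taken, leave it, report the all-treated stage 1 count, and apply the new rule to the final analysis. If more than 25 have been treated by then, apply 8/25 to the first 25 by date of first dose and also report the rate in all treated.

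The cost is a few sentences and a slightly less favourable observed rate. Two prices should be stated openly: the lower power from Step 4 if 40% is an evaluable-only rate, and the small excess over the 10% limit from Step 5 if stage 1 stands as read. Neither calls for a redesign, provided the sponsor accepts the restated power.

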#### 3 STUDY IMPLEMENTATION

#### 3.1 STUDY DESIGN

This is a Phase II single arm, single cohort study that will enroll up to 25 evaluable participants with advanced ASCP that has been previously treated. In order to account for screen failures and inevaluable patients (i.e., participants who are not evaluable for the primary endpoint of response), the accrual ceiling will be set at 55 participants.

Accrual may continue up to 15 treated participants while the primary objective is being determined but no new participants may be accrued once it is known that this criteria has not been met (see Sections 10.3 and 10.5.6).

Initial participants will self-administer Minnelide at 2 mg PO daily on Days 1-21 of each 28 days cycle. Those joining the study after modification dated 3/10/23 will receive Minnelide at 2.5 mg PO daily on Days 1-21 of each 28 days cycle. Participants initially enrolled at the 2 mg dose may be increased to the 2.5 mg dose at the discretion of the study team if they have been tolerating the lower dose (i.e., intrapatient dose escalation is permitted). Treatment will continue for up to 12 cycles (1 year) in the absence of disease progression or unacceptable toxicity. After initiation of treatment, restaging scans will be conducted approximately every 2 cycles or 8 weeks. Optional biopsies will be requested mid-cycle 1 and at time of progression.

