## 10 STATISTICAL CONSIDERATIONS

### 10.1 OBJECTIVES AND ENDPOINTS

OBJECTIVES	ENDPOINTS	JUSTIFICATION FOR ENDPOINTS
Primary		
To determine the single agent antitumor activity (disease control rate) of the anti-superenhancer agent Minnelide in participants with advanced, previously treated ASCP	Assess disease control rate in the study population, where disease control = best response of CR, PR or at least 16 weeks of stable disease	Establishing disease control in 8 or more of 25 participants with advanced previously treated ASCP would be considered clinically significant.
Secondary		
Determine Minnelide safety in participants with advanced, previously treated ASCP	Identify Adverse Events of grade 2 and above (per CTCAE criteria, version 5.0) related to Minnelide that occur from start of treatment to 30 days after last treatment.	Descriptive endpoint to assess toxicity profile of the study drug in this population.
	Assess rate of Serious Adverse Events related to Minnelide that occur from start of treatment to 30 days after last treatment.	
Assess alternative measures of anti- tumor activity	Determine median time until disease progression, switch to a new systemic treatment or death in the treated population. Data cut-off will occur 1 year after last Minnelide treatment.	Descriptive endpoints that may help to determine sample size needed for future Phase 3 study
	Determine median time until death in the treated population. Data cut-off will occur 1 year after last Minnelide treatment.	
	Determine objective response rate of Minnelide.	

OBJECTIVES	ENDPOINTS	JUSTIFICATION FOR ENDPOINTS
Exploratory		
Identify factors that influence participant response to treatment through detailed molecular analysis of participant tumor, serum and blood cell samples acquired at baseline, on-treatment and at time of progression	For each patient with available samples, we will describe the following properties and consider associations with patient response to therapy:	These endpoints have been selected to help understand why the drug may or may not work, to allow better design of future studies in this patient population.
	Tumor genetic mutations at baseline and at time of progression	Do specific genetic profiles give a patient higher or lower likelihood or response? Does treatment change mutational profile?
	Treatment-related change (between pre-treatment baseline and ~C1D15) in:	

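### Does the 95% interval for the primary rate need a named method, a two-stage correction and a stated role?

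*Combined protocol and SAP*

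**What the plan says.** Section 10.5.2 gives the primary rate with an interval that "will be reported along with a 95% two-sided confidence interval". Section 10.5.1 is looser: the fraction among all evaluable participants "will be reported along with a confidence interval". Neither names a method.

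The decision rule is elsewhere. Section 10.3 sets a Simon optimal two-stage design for 20% against 40%, with alpha 0.10 and beta 0.20. At stage 1, "If 0-2 of these 12 participants have clinical benefit, then no further participants will be accrued". At the end, 3 to 7 of 25 is too low to be of interest, and further study is warranted "If there are 8 or more of 25 (32%) who experienced clinical benefit". The endpoint table in 10.1 repeats the mark: "Establishing disease control in 8 or more of 25 participants with advanced previously treated ASCP would be considered clinically significant".

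Because the disease is rare, section 10.3 lets recruitment run on: "trial accrual may continue for up to 15 participants while this determination is being made". Section 3.1 agrees: "Accrual may continue up to 15 treated participants while the primary objective is being determined". Section 10.5.6 uses the first 12 evaluable participants only to decide whether stage 2 opens. Section 10.4 places everyone who receives a dose in the efficacy evaluation.

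**The concern.** Four things look unfinished.

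- **Level.** The design spends 10% on one side, whereas a 95% two-sided interval spends 2.5% per side. A trial that just succeeds, at 8/25, would report an interval containing 20%, and a reader might take that as failure.
- **Method.** With 25 participants the usual methods differ by a few points. At 9/25 the choice settles whether 20% lies inside.
- **Stopping.** An interval built for a fixed sample ignores the stage-1 stop, so its coverage could fall below 95%.
- **Overrun.** After a stage-1 stop, the reported rate could rest on 12 participants or on up to 15.

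If these points mattered, the reported precision could mislead, or an analyst could choose the method or denominator after seeing the data.

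**Working it through.** **Inputs.** From section 10.3: p0 = 0.20, p1 = 0.40, n1 = 12, stop at 0–2, n = 25, success at 8 or more, overrun to 15, one start every 1–2 months. From section 10.5.2: 95%, two-sided. Write b(x; n, p) for the binomial probability.

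**1. The plan's own figure.** The early-stop probability at p0 is the sum of b(x; 12, 0.20) for x = 0, 1, 2, which is 0.06872 + 0.20616 + 0.28347 = 0.5583. The plan states 55.8%.

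**2. The decision rule.** P(success) = sum over x = 3..12 of b(x; 12, p) × P(Y ≥ 8 − x), with Y binomial(13, p). This is 0.0991 at p = 0.20 and 0.8151 at p = 0.40. Both stated error rates hold, and the interval plays no part in them.

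**3. The interval at 8/25.** The Clopper-Pearson limits solve P(X ≥ 8) = 0.025 and P(X ≤ 8) = 0.025 for binomial(25, p), giving 14.9%–53.5%. The stage-wise interval puts the two-stage tail probabilities in their place, ranking early stops lowest, and gives 15.2%–54.5%. The stop therefore moves the lower limit by 0.3 points and the upper by about 1. The 20% rate is inside because of the level: the two-stage p-value at 8/25 is 0.0991, below 0.10 but above 0.025. Naming a method or correcting for the stop would not alter that.

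**4. The method at 9/25.** Lower limits are Wald 17.2%, Clopper-Pearson 18.0%, stage-wise 18.1%, mid-P 19.2%, Jeffreys 19.5%, Agresti-Coull 20.2% and Wilson 20.2%. This is the only count at which the methods disagree about 20%. The trial has succeeded by the count under all of them.

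**5. Coverage under the two-stage design.** Sum the probabilities of all outcomes (x/12 after a stop, s/25 otherwise) whose interval contains the true rate. For Clopper-Pearson this gives 98.3%, 96.9% and 96.5% at true rates of 20%, 30% and 40%. On a grid from 10% to 70% in steps of 0.1 point, it falls below 95% at 15 of 601 points, with a minimum of 94.2% at a true rate of 49.4%.

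**6. What the stage-wise interval costs.**

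| Count | Clopper-Pearson 95% | Stage-wise 95% |
|---|---|---|
| 3/25 | 2.5%–31.2% | 5.5%–48.4% |
| 4/25 | 4.5%–36.1% | 6.5%–48.5% |
| 5/25 | 6.8%–40.7% | 8.1%–48.7% |
| 8/25 | 14.9%–53.5% | 15.2%–54.5% |

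At 3/25 and 4/25 Clopper-Pearson excludes the 40% target and the stage-wise interval does not. Counts of 3 to 5 of 25 occur in 15% of trials at a true 20%.

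**7. The overrun.** Sixteen weeks is 3.68 months, so 1.8 to 3.7 starts are expected while the twelfth outcome matures; the cap of 15 allows at most 3. After a stop at 2/12 the report is 16.7% (2.1%–48.4%) on the first 12. Pooled over 15 it runs from 2/15 = 13.3% (1.7%–40.5%) to 5/15 = 33.3% (11.8%–61.6%). The top of that range is rare: b(2; 12, p) × p³ / P(stop) is 0.28347 × 0.008 / 0.5583 = 0.4% of stopped trials at 20%, and 0.06385 × 0.064 / 0.08344 = 4.9% at 40%. If three extra evaluable participants are assumed at every stop, minimum coverage is 95.1% with the first 12 analysed stage-wise. It is 95.6% when stopped trials are pooled to 15 with Clopper-Pearson and the others analysed stage-wise. Both denominators are valid.

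**The case for a change.** The strongest case for a change is that the text permits too much. A Wald interval satisfies section 10.5.2 as written, and under this design it covers only 91.4% at a true 20% and 87.1% at 40%. Wilson covers 95.5% and 93.5%. The denominator after a stop is also a real choice in a likely setting, since over half of trials stop early at a true 20%. With one, two or three extra evaluable participants, 10.2%, 19.8% or 28.7% of those stopped trials would show 3 or more benefits in all. The précis adds doubt by calling a rate of at least 40% a positive study.

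Part of this stands: the method is not named, and a Wald interval would be a poor choice at this size. But an exact method is the natural one for 25 participants, and it performs well here. On the denominator, section 10.5.1 refers to all evaluable participants and section 10.4 to all who are treated. Both point towards including the later participants, and only the stage-2 decision is confined to 12. Those two sections differ on evaluable against treated, but that is a separate matter. So is the précis wording, which sets no condition on the interval. The overrun also shrinks if anyone is inevaluable, because section 3.1 caps treated participants while stage 1 counts evaluable ones.

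An 80% stage-wise interval would agree with the count rule (20.04%–47.4% at 8/25; lower limit 17.1% at 7/25). It restates that rule and changes no result.

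**Conclusion.** No change to the plan is needed. The count of 8 or more of 25 decides, it is written in two places, and it meets its stated error rates. The interval is reported beside the rate and is not a test. Its inclusion of 20% at 8/25 follows from choosing the conventional 95% level for reporting while designing at alpha 0.10, which is an accepted combination.

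The two-stage effect on an ordinary exact interval is about 1 point or less at 8/25, and the worst coverage found is 94.2%. The stage-wise interval guarantees coverage but gives up the ability to exclude 40% at 3/25 and 4/25, so preferring it is a trade-off and not a correction. The unnamed method and the denominator after a stop are reporting details. Stating the method and showing any participants beyond the first 12 in the results table covers both.

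This rests on the analyst using an exact method, on stages of exactly 12 and 25 evaluable participants, and on the stage-1 decision using the first 12 only. No decision, sample size, error rate or stopping rule depends on the point.

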## 10.5.3 Analysis of the Secondary Endpoints

PFS and OS will be determined using the Kaplan-Meier method and will be reported along with a 95% confidence interval for the median.

Objective response rate (ORR) will be calculated as the percentage of patients with CR or PR as defined by RECIST 1.1 criteria.

Analysis of safety is as described in the Section 10.5.4.

### **10.5.4 Safety Analyses**

The fraction of participants who experience a toxicity, by grade and type of toxicity, will be tabulated.

